13.1. General Principles

In general, descriptive statistics will be used to summarize study outcomes. For continuous variables, the number of available observations, mean, standard deviation, median, minimum and maximum values will be provided. For categorical variables, frequency and percentage will be used. Unless otherwise specified, statistical assessments will be based on two-sided tests at an alpha level of 0.05, which include Student-t or Wilcoxon rank-sum test for continuous variables, and Chi-square or Fisher's exact test for

categorical variables. Other statistical methods may be used as appropriate. Statistical analysis will be performed using SAS Version 9.2 or higher (SAS Institute Inc., Cary, NC) or other valid statistical software.

13.2. Sample Size Determination

The proposed sample size of up to 100 subjects is considered adequate for the study objective. From published data, a complete response rate of 80%-90% of the RFA treatment is expected at 12 months post-treatment for the subject population (18). With 100 study subjects, a precision (half 95% CI width) of 6%-8% will be achieved for estimating the primary endpoint of complete response rate. For safety, a sample of 100 subjects will have greater than a 99% chance to detect a rare event of 5% incidence or an 85% chance to detect a rare event of 2% incidence. The NIH defines an acceptable dropout rate at 20% or less. However, over 70% of all high-quality clinical studies in China had a dropout rate lower than 10%. For example, the dropout rate at CICAMS was 3% in a previous ESCN study.

13.3. Analysis Populations

The primary analysis will be based on a per-protocol basis. Subjects who enrolled into the study (a patient is defined as enrolled after introduction of RFA catheter at primary RFA), and had valid study outcomes with no major protocol violations will be included in the analysis. Only the 100 cohort patients will be included for primary analysis.

Additional analyses based on subsets of the study subjects or combining run-in subjects may be performed to provide further support to the study results.

All enrolled study subjects will be included in the safety analysis.

13.4. Effectiveness Analysis

The primary effectiveness will be measured as the percentage of subjects with complete response within the treatment area. The response rates and 95% confidence intervals will be summarized. Run-in subjects will be summarized separately.

13.5. Safety Analysis

For safety analyses, adverse events will be summarized using frequency counts and percentages. Descriptive statistics will be provided by event type, severity and relationship to study procedures and devices. Event rates along with 95% confidence intervals will be provided based on subject or event. Individual listings of adverse events, including event type, start date, duration, severity, and device-relatedness will be provided as appropriate.

Safety will be closely monitored during the course of the study. If the incidence of severe or serious adverse events is higher than expected (stricture/stenosis requiring dilation >10%, any mucosal laceration requiring intervention, any perforation, any bleed or infection requiring intervention, or any other severe or serious unexpected adverse event), or a statistically significant trend is observed, the medical advisors will notify the sponsor, review all available data, and make a recommendation regarding continuation of the study.

13.6. Additional Analyses

Subgroup analysis will be performed for potential confounding factors such as study center, age, gender, use of escape treatment, and disease severity (moderate vs. high grade). A multivariate analysis will be conducted to further examine the predictors of compete response. Potential predictive factors to be considered will include but not limited to: age, gender, and grade (MGIN vs. HGIN).

The number and proportion of subjects eligible for and compliant with each follow-up examination will be presented. Subjects who withdraw from the study will be tabulated with reasons for withdrawal. Sensitivity analysis for discontinuations or missing data will be conducted to assess the robustness of study results which may include last observation carried forward, multiple imputations, and tipping point analysis, as appropriate.

For study monitoring and learning curve evaluations, summary data will be provided for the primary and secondary endpoints between the first half of subjects enrolled versus the second half of subjects enrolled for each site and overall. Furthermore, CR-rates at 3 and 12 months for the run-in cases will be analyzed.

Additionally, interim data summaries may be performed, as needed, for requirements related to abstract submission, IRB requests, or Independent Medical Advisor requests. Considering the feasibility nature of the study, no multiplicity adjustment is considered. Efficacy and safety will be specifically assessed after enrollment of up to 50 patients.

Any departure or deviation from these planned statistical methodologies will be documented and discussed in the Statistical Analysis Plan (SAP) that will include the statistical rationale for divergence.

14. Ethics

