8.2. Subject Enrollment

Up to 100 subjects are planned for enrollment in the primary analysis cohort. With up to 10 sites and 1-2 endoscopists at each site, up to 50 'run-in' patients will be included in this study. Run-in patients are defined as up to 5 patients for each endoscopist that is inexperienced with RFA or has had no RFA onsite training from CICAMS. Data from the run-in patients will be analyzed separately from the cohort.

Patients shall be reviewed according to the following inclusion and exclusion criteria. An answer of "no" to any inclusion criterion or an answer of "yes" to any exclusion criterion disqualifies a subject from participating in this study. Complete the **Eligibility CRF**.

Definitive eligibility can only be assured during the primary RFA endoscopy, e.g. if a severe stricture or a non-flat abnormality is present, patient is not eligible. Therefore, the subject is considered as enrolled after insertion of the RFA catheter.

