7.2. General Methodology

In general, descriptive statistics will be used to summarize study outcomes. For continuous variables, the number of available observations, mean, standard deviation, median, minimum and maximum values will be provided. For categorical variables, frequency and percentage will be used. Unless otherwise specified, statistical assessments will be based on two-sided tests at an alpha level of 0.05, which include Student-t or Wilcoxon rank-sum test for continuous variables, and Chi-square or Fisher's exact test for categorical variables. Other statistical methods may be used as appropriate. Statistical analysis will be performed using SAS Version 9.2 or higher (SAS Institute Inc., Cary, NC) or other valid statistical software.

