7.11. Additional Analyses

Subgroup analysis will be performed for potential confounding factors such as study center, age, gender and disease severity (moderate vs. high grade). A multivariate analysis will be conducted to further examine the predictors of complete response. Potential predictive factors to be considered will include but not limited to: age, gender, and grade (MGIN vs. HGIN).

The number and proportion of subjects eligible for and compliant with each follow-up examination will be presented. Subjects who withdraw from the study will be tabulated with reasons for withdrawal. Sensitivity analysis for discontinuations or missing data will be conducted to assess the robustness of study results which may include last observation carried forward, multiple imputations, and tipping point analysis, as appropriate.

For study monitoring and learning curve evaluations, summary data will be provided for the primary and secondary endpoints between the first half of subjects enrolled versus the second half of subjects

This document is electronically controlled. Printed copies are considered uncontrolled.

Confidential

12JUL2017

enrolled for each site and overall. Furthermore, CR-rates at 3 and 12 months for the run-in cases will be analyzed.

8. Validation Requirements

Primary and secondary endpoints will be validated by level I validation and the rest of the tables, listings and figures will be validated by level II validation.

Level I: The peer reviewer independently programs output and then compares the output with that generated by the original Statistical Programmer.

Level II: The peer reviewer reviews the code; where appropriate, performs manual calculations or simple programming checks to verify the output.

9. Reference

This document is electronically controlled. Printed copies are considered uncontrolled.

Confidential

12JUL2017

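### The overall learning-curve table splits subjects by enrolment order, so it mixes within-endoscopist learning with change in operator mix; low priority

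*Protocol*

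**What the plan says.** CIP 13.6 names two purposes, monitoring the study and evaluating the learning curve, and sets one contrast: "summary data will be provided for the primary and secondary endpoints between the first half of subjects enrolled versus the second half of subjects enrolled", both by site and overall. SAP 7.11 sets the same contrast, "between the first half of subjects enrolled versus the second half of subjects", in the same terms. Neither document orders cases by endoscopist, adjusts for operator, defines the halves further, or says whether run-in subjects count in them. No test is named for this table. SAP 7.2 sets only a general default: "statistical assessments will be based on two-sided tests at an alpha level of 0.05" unless otherwise specified.

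CIP 13.6 adds that "CR-rates at 3 and 12 months for the run-in cases will be analyzed". Run-ins are defined in two ways:

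- CIP 8.2: "Run-in patients are defined as up to 5 patients for each endoscopist that is inexperienced with RFA or has had no RFA onsite training from" the lead study site (CICAMS). Other endoscopists have no run-ins.
- SAP 7.9 and 7.9.2 (item 5): the first 5 subjects of every endoscopist. The SAP says it supports CIP v4; the CIP supplied is v7.

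CIP 8.2 allows up to 10 sites with 1-2 endoscopists each. It analyses run-in data separately from the cohort of up to 100.

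**The concern.** A learning-curve table should show whether results improve as an operator gains experience. The run-in rule recognises this, because it defines experience per endoscopist. The overall half-split drops that unit.

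Under CIP 8.2 an experienced endoscopist contributes to the cohort from the first case, and a new one only after the run-ins. If both kinds take part and the halves are formed from the cohort, the second half holds relatively more cases from new endoscopists. The tabulated difference then combines two things: change within operators, and change in who is operating. It can understate or hide learning, or show a trend when no operator has changed. At stake is the interpretation of one planned secondary table, not the primary result.

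**Working it through.** **1. Figures in the plan.** The plan gives none for this analysis. Its precision statement for the primary endpoint (CIP 13.2) does reproduce: 1.96 × √(0.8 × 0.2/100) = 7.8% and 1.96 × √(0.9 × 0.1/100) = 5.9%, against the stated 6%-8%.

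**2. Inputs.** From the documents: 100 cohort subjects, up to 10 sites, up to 5 run-ins per new endoscopist, enrolment expected in 12 months (CIP 6.1). Assumed: 10 endoscopists, 5 of them new; 15 cases a year each (1.25 a month); all open at month 0; 5 run-ins per new endoscopist; halves formed from the cohort. Total cases are 100 + 25 = 125 at 12.5 a month, so enrolment takes 10 months, which is compatible with the plan.

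**3. Operator mix with steady accrual.** Five run-ins take 5/1.25 = 4 months.

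- Months 0-4: experienced endoscopists only, 5 × 1.25 × 4 = 25 cohort cases.
- Months 4-6: all ten, 25 cases, 12.5 from each group. This completes the first half.
- Months 6-10: 50 cases, 25 from each group.

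The experienced share is 37.5/50 = 75% in the first half and 25/50 = 50% in the second. With random arrivals, simulation gives about 74% and 51%.

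**4. What the table would show.** By month 10 an experienced endoscopist has 12.5 cohort cases and a new one 7.5. Pooling within-endoscopist halves in proportion to cases gives the groups weights of 62.5% and 37.5%.

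*(a) Everyone learns: CR 70% in each endoscopist's first 5 cohort cases, 95% after.*
- Enrolment halves: first (37.5 × 70 + 12.5 × 95)/50 = 76.25%; second (12.5 × 70 + 37.5 × 95)/50 = 88.75%; difference +12.5.
- Own-case halves: experienced 75% to 95% (+20); new 70% to 86.7% (+16.7); pooled 0.625 × 20 + 0.375 × 16.7 = +18.75.

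*(b) Only new endoscopists learn: 65% through case 10 counted from the first run-in (their first 5 cohort cases), 92% after; experienced 92% throughout.*
- Enrolment halves: each holds 37.5 cases at 92% and 12.5 at 65%, so both are 85.25%; difference 0.
- Own-case halves: new 65% to 83% (+18), experienced 0; pooled 0.375 × 18 = +6.75.

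*(c) No learning: experienced 92%, new 75%.*
- Enrolment halves: 0.75 × 92 + 0.25 × 75 = 87.75%, then 0.50 × 92 + 0.50 × 75 = 83.5%; difference -4.25.
- Own-case halves: 0.

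| Pattern | Enrolment halves, steady / random arrivals | Own-case halves, steady / random arrivals |
|---|---|---|
| (a) | +12.5 / about +12 | +18.75 / about +18 |
| (b) | 0 / about +1 or less | +6.75 / about +7 |
| (c) | -4.25 / about -4 | 0 / 0 |

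**5. Opening order.** Spread openings over 6 months in pattern (b). If order is unrelated to experience, the enrolment-half difference stays near zero (about +0.5). If all new endoscopists open after all experienced ones, it is about -6. If new endoscopists open first, it is about +6.

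**6. By-site tables.** With 10 equal sites each compares about 5 with 5. The 95% half-width is 1.96 × √(2p(1-p)/5), which is 50 points at p = 0.8 and 37 at p = 0.9. The overall 50 v 50 contrast has 16 and 12 points. At a one-endoscopist site the by-site halves are the endoscopist's own halves. At a two-endoscopist site where the two work in sequence on the same curve, a true +10 can appear as 0.

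**The case against.** The strongest reply is that the same sentence plans by-site tables, and CIP 8.2 allows one endoscopist per site. At such sites the by-site split is already the within-endoscopist split, and the small strata are no smaller than those of the proposed fix. That stands. What remains is that the plan does not pool these tables, each is too imprecise alone, and two-endoscopist sites mix operators.

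Other replies also hold in part:

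- The table is descriptive. Power and rejection rates would apply only if the default tests were used, so the point concerns the tabulated difference.
- Performance of new operators is reported directly, through run-in CR at 3 and 12 months and sustained CR (secondary endpoint 5). That does not compare the same endoscopists' later cases.
- The mix shift is conditional. Fifty run-ins at 5 each is ten new endoscopists; if all are new, the run-in asymmetry disappears. It also disappears under the SAP definition.
- Pattern (a) places the learning step near the middle of each endoscopist's cohort cases, which favours the own-case split.

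A reader might infer that the overall table measures only operator mix, or that it will reverse the sign of real learning. The documents support neither. When all endoscopists enter the cohort together and accrue evenly, the table returns the within-operator change. In the illustration, reversal needs new endoscopists to open later as well, and no opening schedule is given. Nor does any objective or endpoint make this table the basis for judging whether the regimen transfers to new operators.

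**Conclusion.** The point holds in limited form. As the overall learning-curve summary, enrolment-order halves confound within-operator learning with operator mix. Under the CIP v7 run-in rule, with both experienced and new endoscopists, the mix moves even if all open together. In the illustration the tabulated difference is off by roughly 4 to 6 points: 12 instead of 18, about 1 or less instead of 7, and -4 instead of 0.

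These sizes rest on the assumed number of new endoscopists, accrual rate, opening dates and CR values, none of which the documents give, and on halves formed from the cohort without run-ins. The analysis is secondary and descriptive and the primary endpoint is unaffected, so the priority is low.

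**What to change.** 1. Reconcile the run-in definitions in CIP 8.2 and SAP 7.9/7.9.2, because they decide which early cases stay in the cohort.
2. In CIP 13.6 and SAP 7.11, define the learning-curve halves as the first and second half of each endoscopist's own cohort cases. Number cases from that endoscopist's first study case, with run-ins included in the numbering and flagged.
3. Pool across endoscopists with a Mantel-Haenszel risk difference stratified by endoscopist, with a 95% CI.
4. For endoscopists with run-ins, show run-in, early-cohort and late-cohort CR side by side.
5. Keep the enrolment-order halves, labelled as study monitoring only.

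The cost is about one sentence in each document and one extra table. Endoscopist and case order are already needed to identify run-ins. The downside is that strata with few cases or no failures add little information, so the pooled estimate will still be imprecise. The primary cohort and primary analysis do not change.

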14.1. Statement(s) of Compliance

This clinical investigation will be conducted in accordance with the ethical principles that have their origin in the Declaration of Helsinki, ISO 14155:2011 (Clinical Investigation of Medical Devices for Human Subjects – Good Clinical Practice), and any regional or national regulations, as appropriate. The principles of the Declaration of Helsinki have all been implemented by means of the

Medtronic Confidential

patient informed consent process, EC approval, study training, clinical study registration, preclinical testing, risk benefit assessment, and publication policy. Pediatric, legally incompetent, or other vulnerable subjects are not eligible for the study.

The clinical investigation will not begin until all necessary approvals/favorable opinions are obtained from the appropriate EC/IRBs or regulatory authority, as appropriate. Should an EC/IRB or regulatory authority impose any additional requirements, they will be followed.

Information regarding the study and study data will be made available via publication on clintrials.gov. Additionally, the results of this study will be submitted for publication in an appropriate journal.

14.2. Protocol Compliance

No changes to the protocol will be permitted without the written approval from the Sponsor and the IRB/EC. The investigator must notify the Sponsor and the reviewing IRB/EC of any deviation from the Investigational Plan when specific to the protection of the life or physical well-being of a subject in an emergency. Such notice must be given as soon as possible, but in no event later than 5 working days after the emergency has occurred. Except in such an emergency, prior written approval by the Sponsor and the site IRB/EC is required for changes in or deviations from the Plan. All deviations will be reported per the site's IRB/EC deviation policy. Should any deviations from the Investigational Plan occur, these will be reviewed by the Sponsor for their clinical significance. If the event is performed without written approval from all parties, the investigator may be terminated from the study.

15. Study Administration

15.1. Monitoring

Site visits will be conducted by an authorized Sponsor representative to inspect study data, subjects' medical records, and CRFs in accordance with the respective local and national government regulations and guidelines (if applicable). The Study Investigator and the investigating site will permit authorized clinical research personnel and clinical monitors from the Sponsor and/or designee(s) employed by the Sponsor to review completed CRFs, IRB decisions, and Investigator, clinical site records, and facilities relevant to this study at regular intervals throughout the study per the monitoring plan. Additionally, subject charts and clinical records will be requested and reviewed so that protocol adherence and source documentation can be verified. The accuracy and quality of the data obtained from the investigator and maintained by the Sponsor will be confirmed through a structured program of clinical field auditing and internal review detailed in the monitoring plan. In instances where data protection regulations prohibit the direct examination of hospital records by the study Sponsor or designee(s), the Investigator will cooperate in a system of source data verification with the Sponsor. Monitoring may be performed with in person visits or remotely, when applicable.

Medtronic Confidential

To ensure the rights, safety, and welfare of study subjects are being maintained, the monitor will review training records to ensure all study staff are trained on the study protocol and use of the study devices. If the monitor discovers that an investigator is not complying with the signed Investigator Agreement, the investigational plan, applicable laws, or any conditions of approval imposed by the reviewing IRB or Competent Authority, the monitor will report to the Sponsor and take such steps necessary to promptly secure compliance. If compliance cannot be secured, device shipments to the investigator may be discontinued and the investigator's participation in the investigation terminated. The monitor shall also require such an investigator to dispose of or return the device, unless this action would jeopardize the rights, safety, or welfare of a subject.

15.2. Data Management

This study will utilize an electronic database and eCRF. All data requested on the CRF are considered required. Data points not collected and/or recorded will be considered deviations unless otherwise specified. The Principal Investigator must ensure the accuracy and completeness of the recorded data and then provide his/her signature on the appropriate CRFs. The Investigator's electronic signature for specific CRFs will be documented in compliance with local regulations. Changes to data previously submitted to the sponsor will require a new electronic signature by the Investigator to acknowledge/approve the changes.

Visual and/or computer data review will be performed to identify possible data discrepancies. Manual and/or automatic queries will be created in the Oracle remote data capture (RDC) system and will be issued to the site for appropriate response. The site staff will be responsible for resolving all queries in the database.

15.3. Direct Access to Source Data/Documents

The investigator must agree to the inspection of study-related records by the Regulatory Authority/Sponsor representatives, and must allow direct access to source documents to the Regulatory Authority/Sponsor representatives/EC representatives.

15.4. Confidentiality

All records identifying the subject will be kept confidential and, to the extent permitted by the applicable laws and/or regulations, will not be made publicly available.

Subject names will be kept confidential. Only the subject number and initials will be recorded in the CRF, and if the subject name appears on any other document, it must be obliterated. In cases where the local law does not allow using the subject initials, an identifying number will be assigned.

A Subject Log will be maintained in a secure locked location by the Investigator to enable tracing of specific case study numbers to subjects, in the event required.

Study findings stored on a computer will be stored in accordance with local data protection laws. The subjects will be informed in writing that representatives of the sponsor, IRBs, or Regulatory Authorities may inspect their medical records to verify the information collected, and that all personal information made available for inspection will be handled in strictest confidence and in accordance with local data protection laws.

Subjects will also be informed that information regarding the study that does not include subject identifiers will be posted on clinicaltrials.gov.

If the results of the trial are published, the subject's identity will remain confidential.

The investigator will maintain a list to enable subjects' records to be identified.

